8.3 Pharmacodynamic Assessments

Venous blood samples will be collected for PD assessments at Day 1 (Visit 2), Week 4 (Visit 3), Week 8 (Visit 4), Week 12 (Visit 5)/ET, and at the follow-up visit (Week 15 [Visit 6]). Subjects should be fasted (defined as nothing by mouth except water [up to 1 hour before study drug intake] for at least 10 hours prior to study visit. During the postdose assessment period, the subject may eat and drink, provided this is done at least 1 hour after dosing.

Samples will be taken predose at Day 1 (Visit 2), Week 8 (Visit 4), and Week 12 (Visit 5)/ET, as well as predose and 3 hours postdose at Week 4 (Visit 3). The Week 4 (Visit 3) 3-hour postdose PD sample should be shifted to a later date in cases where the subject cannot accommodate the PK sampling schedule at that visit. The PD sample should be taken at the same time as the 3-hour postdose PK sample (see Section 8.2). A PD sample will be taken at the follow-up visit (Week 15 [Visit 6]) as well. Markers include LH, FSH, E2, and SHBG.

The exact date and time of blood sampling must be recorded in the source documents and on the eCRF. Plasma will be collected and handled as specified in the central laboratory manual. After appropriate labeling, the plasma samples will be stored below -70°C at the study site. Thereafter, the frozen plasma samples will be transported/shipped on dry ice to the central laboratory for collection and storage below -70°C until analysis.

Further procedures for sample collection, shipment, processing, and storage are described in the laboratory manual.

8.4 Pharmacogenomic Assessments

Optional pharmacogenomic sampling is scheduled to occur at Week 12 (Visit 5)/ET; however, sampling can occur any time after subjects sign the PGX ICF and are enrolled into the study. Pharmacogenomic samples will be stored for potential future analysis. Any PGX sample taken during screening will be destroyed in the event of a screen failure.

9 SAFETY ASSESSMENTS

Safety variables will include adverse events, C-SSRS, endometrial health assessment (transvaginal ultrasound ± endometrial biopsy), clinical laboratory tests, plasma bone density marker concentrations, ECGs, vital signs, and physical examinations, as described in the following sections.

9.1 Adverse Events

An adverse event is defined as any untoward medical occurrence in a clinical investigation subject administered a pharmaceutical product, which does not necessarily have a causal relationship with this treatment. An adverse event can therefore be any unfavorable and/or unintended sign (including an abnormal laboratory finding), symptom, or disease temporally associated with the use of an investigational medicinal product, whether or not related to the investigational medicinal product. All adverse events, including observed or volunteered problems, complaints, or symptoms, are to be recorded on the appropriate eCRF.

Adverse events, which include clinical laboratory test variables, will be monitored and documented from the time of informed consent until study participation is complete. Subjects should be instructed to report any adverse event that they experience to the Investigator. Investigators should make an assessment for adverse events at each visit (excluding Visits 2A, 3A, and 4A) and record the event on the appropriate adverse event eCRF.

Wherever possible, a specific disease or syndrome rather than individual associated signs and symptoms should be identified by the Investigator and recorded on the eCRF. However, if an observed or reported sign or symptom is not considered a component of a specific disease or syndrome by the Investigator, it should be recorded as a separate adverse event on the eCRF. Additionally, the condition that led to a medical or surgical procedure (eg, surgery, endoscopy, tooth extraction, or transfusion) should be recorded as an adverse event, not the procedure.

Any medical condition already present at the screening visit will be recorded as medical history and should not be reported as an adverse event. Any medical condition or signs or symptoms present at screening that change in severity or seriousness at any time during the study should be reported as an adverse event.

Clinically significant abnormal laboratory or other examination (eg, ECG) findings that are detected during the study or are present at the screening visit and significantly worsen during the study should be reported as adverse events. The Investigator will exercise his or her medical and scientific judgment in deciding whether an abnormal laboratory finding or other abnormal assessment is clinically significant. Clinically significant abnormal laboratory values occurring during the clinical study will be followed until repeat tests return to normal, stabilize, or are no longer clinically significant. Any abnormal test that is determined to be an error does not require reporting as an adverse event.

9.1.1 Unexpected Adverse Drug Reaction

An unexpected adverse drug reaction is defined as an adverse reaction, the nature or severity of which is not consistent with the applicable product information.

9.1.2 Adverse (Drug) Reaction

All noxious and unintended responses to a medicinal product related to any dose should be considered an adverse drug reaction. “Responses” to a medicinal product means that a causal relationship between a medicinal product and an adverse event is at least a reasonable possibility, ie, the relationship cannot be ruled out.

9.1.3 Assessment of Adverse Events by the Investigator

The Investigator will assess the severity (intensity) of each adverse event as mild, moderate, or severe, and will also categorize each adverse event as to its potential relationship to study drug using the categories of yes or no.

Assessment of Severity:

Mild – An event that is easily tolerated and generally not interfering with normal daily activities.

Moderate – An event that is sufficiently discomforting to interfere with normal daily activities.

Severe – An event that is incapacitating with inability to work or perform normal daily activities.

Causality Assessment:

The relationship of an adverse event to the administration of the study drug is to be assessed according to the following definitions:

No (unrelated, not related, no relation) – The time course between the administration of study drug and the occurrence or worsening of the adverse event rules out a causal relationship and another cause (concomitant drugs, therapies, complications, etc.) is suspected.

Yes (related) – The time course between the administration of study drug and the occurrence or worsening of the adverse event is consistent with a causal relationship and no other cause (concomitant drugs, therapies, complications, etc.) can be identified.

The definition implies a reasonable possibility of a causal relationship between the event and the study drug. This means that there are facts (evidence) or arguments to suggest a causal relationship.

The following factors should also be considered:

- The temporal sequence from study drug administration-
 - The event should occur after the study drug is given. The length of time from study drug exposure to event should be evaluated in the clinical context of the event.
- Underlying, concomitant, intercurrent diseases-
 - Each report should be evaluated in the context of the natural history and course of the disease being treated and any other disease the subject may have.
- Concomitant drug-
 - The other drugs the subject is taking or the treatment the subject receives should be examined to determine whether any of them might be recognized to cause the event in question.

- Known response pattern for this class of study drug-
 - Clinical and/or nonclinical data may indicate whether a particular response is likely to be a class effect.
- Exposure to physical and/or mental stresses-
 - The exposure to stress might induce adverse changes in the recipient and provide a logical and better explanation for the event.
- The pharmacology and PK of the study drug-
 - The known pharmacologic properties (ADME) of the study drug should be considered.

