6.2 Safety Variables

Safety variables will include the following:

- Incidence and severity of treatment-emergent adverse events (TEAEs);
- Endometrial health assessment (transvaginal ultrasound ± endometrial biopsy);
- Vital signs (sitting systolic and diastolic blood pressure and pulse rate);
- Laboratory tests (hematology, biochemistry, urinalysis, and coagulation);
- 12-lead electrocardiogram (ECG) parameters;
- Plasma bone density marker concentrations;

- Physical examinations; and
- Columbia Suicide Severity Rating Scale (C-SSRS).

A TEAE is defined as an adverse event observed after starting administration of study drug through 7 days after the last dose of study drug. If the adverse event occurs on the day of the first dose and the onset time is on or after the time of the first dose of study drug or the onset time is missing, then the adverse event will be considered treatment emergent. If the adverse event occurs on the day of first dose and the onset time is before the time of the first dose of study drug, then the adverse event will not be considered treatment emergent. If a subject experiences an event both during the pre-investigational period that continues into the investigational period, the event will be considered as TEAE only if it has worsened in severity (i.e. it is reported with a new start date).

A drug-related TEAE is defined as any TEAE related to study treatment as assessed by the investigator or with missing assessment of the causal relationship.

Other safety endpoints will be considered treatment emergent if observed after starting administration of study drug through 1 day after the last dose of study drug.

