7.5.1 Adverse Events

Summaries and listings of SAEs and Serious TEAEs include SAEs upgraded by the sponsor based on review of the Sponsor's list of Always Serious terms if any upgrade was done.

The coding dictionary for this study will be MedDRA. It will be used to summarize AEs by SOC and PT.

An overview table will include the following details:

- Number of TEAEs,
- Number and percentage of subjects with TEAEs,
- Number of drug related TEAEs,
- Number and percentage of subjects with causally drug related TEAEs,
- Number of serious TEAEs,
- Number and percentage of subjects with serious TEAEs,
- Number of serious drug related TEAEs,
- Number and percentage of subjects with serious drug related TEAEs,
- Number of TEAEs leading to permanent discontinuation of study drug,
- Number and percentage of subjects with TEAEs leading to permanent discontinuation of study drug,
- Number and percentage of subjects with TEAEs leading to study drug interruption, and
- Number of deaths.

The number and percentage of subjects with TEAEs, as classified by SOC and PT will be summarized for each treatment group. Summaries will be provided for:

- TEAEs,
- drug related TEAEs,
- serious TEAEs,
- drug related serious TEAEs,

- TEAEs leading to permanent discontinuation of study drug,
- drug related TEAEs leading to permanent discontinuation of study drug,
- TEAEs excluding serious adverse events that equal to or exceed a threshold of 5% in any treatment group, and
- common TEAEs that equal to or exceed a threshold of 5% in any treatment group.

The number and percentage of subjects with TEAEs, as classified by PT only, will be summarized for each treatment group.

The number of TEAEs and the number and percentage of subjects with TEAEs, as classified by SOC and PT will also be summarized by severity and by relationship to study drug. In the subject count, if a subject has multiple TEAEs with the same SOC or PT, but with differing severity or relationship, then the subject will be counted only once with the worst severity and highest degree of relationship, however, if any of the severity or relationship values are missing then the subject will be counted only once with missing severity or relationship. In the adverse event count, the adverse events will be presented in each category they were classified to. Drug related TEAEs will be presented in a similar way by severity only.

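### The yes/no causality definitions in Protocol 9.1.3 leave two kinds of event in neither class and set a narrower test than 9.1.2, so relatedness may be assigned inconsistently

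*Protocol*

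**What the plan says.** Protocol 9.1.3 tells the investigator to "categorize each adverse event as to its potential relationship to study drug using the categories of yes or no". There is no middle or unassessable category.

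- *No* applies when the time course "rules out a causal relationship and another cause (concomitant drugs, therapies, complications, etc.) is suspected".
- *Yes* applies when the time course "is consistent with a causal relationship and no other cause (concomitant drugs, therapies, complications, etc.) can be identified".

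The section then adds: "The definition implies a reasonable possibility of a causal relationship between the event and the study drug". It closes with six factors to weigh, among them other diseases, other drugs and exposure to stress.

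Protocol 9.1.2, immediately before, defines an adverse drug reaction by a different test: causality "is at least a reasonable possibility, ie, the relationship cannot be ruled out".

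SAP 6.2 takes the investigator's answer into the analysis. A drug-related TEAE is "any TEAE related to study treatment as assessed by the investigator or with missing assessment of the causal relationship". SAP 7.5.1 builds several tables on that definition. In the table by relationship, however, "if any of the severity or relationship values are missing then the subject will be counted only once with missing severity or relationship".

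**The concern.** A binary field needs two definitions that together cover every event. Here each definition joins two conditions with *and*, and neither is the negation of the other, so some events satisfy neither.

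One of the uncovered groups is the one where causality judgement matters most: plausible timing with a competing explanation. It is unlikely to be rare. Protocol 5.6.2 allows analgesics, stable antidepressants, antihypertensives and thyroid replacement, occasional sedatives and prescribed opiates. For raised transaminases, an event of special interest in 9.15, Appendix D lists many possible confounders. Three of the six factors in 9.1.3 (other disease, other drugs, stress) send the investigator looking for alternatives. On the literal *Yes* text, finding one defeats *Yes*.

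At stake is the meaning of the drug-related tables. The protocol synopsis plans about 55 sites (SAP 7.10.2 says about 48). If they fill the gap in different ways, the tables mix different rules.

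**Working it through.** No arithmetic applies. The check crosses the two conditions used in 9.1.3 and applies each section's test to every combination. Timing is taken as either consistent with causality or excluding it. An indeterminate time course would only widen the gap.

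| | Timing | Other cause | Class under 9.1.3 | Under 9.1.2 |
|---|---|---|---|---|
| 1 | Consistent | None | *Yes* | Reaction |
| 2 | Consistent | Present | Neither | Reaction, unless the other cause rules the drug out |
| 3 | Excludes drug | Suspected | *No* | Not a reaction |
| 4 | Excludes drug | None | Neither | Not a reaction |

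Two of the four combinations have no class. In combinations 1 and 3 the sections agree. In combination 2 they conflict: an identifiable alternative does not by itself rule the drug out, so an event can be a reaction under 9.1.2 and still fail *Yes* in 9.1.3.

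Next, the effect on the drug-related count, measured against 9.1.2, for each way a gap event might be recorded:

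- Combination 2 recorded *No*: under-count, unless the other cause rules the drug out.
- Combination 2 recorded *Yes*: no under-count.
- Combination 2 left blank: counted as drug-related under SAP 6.2, but shown as missing in the by-relationship table of SAP 7.5.1.
- Combination 4 recorded *No*: no error.
- Combination 4 recorded *Yes* or left blank: over-count in the tables that use the SAP 6.2 definition.

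Finally, where the field is used:

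- **SAP 6.2 and 7.5.1.** The counts of drug-related and serious drug-related TEAEs, drug-related discontinuations, and the splits by relationship all depend on it.
- **Protocol 9.3.** Serious events from consent to 30 days after the last dose are reported whatever the causality. After that, the duty covers only those the investigator considers related.
- **Protocol 9.4.** The liver and platelet criteria refer to confirmed study-related changes. The term is not defined there or linked to 9.1.3, so dependence is possible but not stated.
- **Not dependent.** The all-causality TEAE, serious TEAE and discontinuation summaries do not use the field. Nor do the events of special interest in 9.15.

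**The case against.** The best defence is to read 9.1.3 as a whole. Its reasonable-possibility sentence echoes 9.1.2, and a list of factors to weigh would be pointless if any identifiable alternative settled the matter. A sensible investigator would apply judgement. That has force as a guess at intent, but the sentence leaves the no-other-cause condition in place. The gloss that follows it asks for evidence or arguments in favour of causality, which is not the same test as being unable to exclude it. The text still gives an investigator no class for combination 2.

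A reader might go further and infer that drug-related events will be under-counted. The documents do not support that:

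- The *No* text is as strict as the *Yes* text. It requires timing that "rules out a causal relationship and another cause", so a literal reader cannot record *No* for an event with consistent timing either.
- A blank counts as drug-related under SAP 6.2, although the protocol instructs a yes or no, so blanks should be few.
- Combination 4 can push the count upwards.

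A reader might also infer that expedited reporting and the stopping criteria are compromised. Serious events up to 30 days after the last dose reach the safety group regardless of causality, and nothing in 9.6 confines the sponsor to events that the investigator marked *Yes*. In 9.4 the seizure criterion carries its own attribution test, and the criterion on deaths and other serious events has no relatedness condition. Only the liver and platelet criteria could be touched, and only if study-related is meant in the 9.1.3 sense.

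It is also fair that the same wording applies in every arm of a double-blind trial, so the all-causality comparison with placebo stands.

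**Conclusion.** The concern holds as an inconsistency between definitions. The two classes in 9.1.3 are not exhaustive, and its *Yes* text conflicts with 9.1.2 and with the reasonable-possibility sentence in its own section. Inconsistent classification across sites is the supported consequence. Under-counting is a conditional risk: it follows if investigators apply *Yes* strictly and record *No* by default.

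The size cannot be computed. Two of four combinations is a count of logical cases, not a share of events, and the documents do not say how often each arises or how sites were told to resolve them. The conclusion assumes that no eCRF guidance outside these documents already closes the gap. The damage is confined to the drug-related subset tables, serious events first arising after the 30-day window and, possibly, two of the criteria in 9.4.

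**What to change.** Rewrite the two definitions in 9.1.3 as complements on the 9.1.2 standard:

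- *Yes*: a causal relationship is at least a reasonable possibility, meaning that it cannot be excluded, whether or not another cause is present.
- *No*: there is no reasonable possibility of a causal relationship.

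Keep the list of factors as aids to that single judgement, and put the same wording in the eCRF completion guidance. Section 9.4 should be reconciled with 9.1.3 so that readers can tell whether study-related means this category. That concerns the term only, not the criteria.

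The cost is two sentences in the protocol and a matching line in the eCRF guidance. The downside is that somewhat more events may be classed as related. No change to the SAP's drug-related definition is needed. If events have already been recorded under the present text, the study report should say so and rest the safety comparison on the all-causality tables.

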9.2 Serious Adverse Events

An adverse event or adverse reaction is considered serious if, in the view of either the Investigator or Sponsor, it results in any of the following outcomes:

- Death,
- A life-threatening adverse event,
 - NOTE: An adverse event or adverse reaction is considered “life-threatening” if, in the view of either the Investigator or Sponsor, its occurrence places the subject at immediate risk of death. It does not include an event that, had it occurred in a more severe form, might have caused death.
- Requires hospitalization or prolongation of existing hospitalizations,
 - NOTE: Any hospital admission with at least 1 overnight stay will be considered an inpatient hospitalization. An emergency room visit without hospital admission will not be recorded as a SAE under this criterion, nor will hospitalization for a procedure scheduled or planned before signing of informed consent. However, unexpected complications and/or prolongation of hospitalization that occur during elective surgery should be recorded as adverse events and assessed for seriousness. Admission to the hospital for social or situational reasons (ie, no place to stay, live too far away to come for hospital visits) will not be considered inpatient hospitalizations.
- A persistent or significant disability/incapacity or substantial disruption of the ability to conduct normal life functions,
- A congenital anomaly/birth defect, or
- An important medical event.
 - NOTE: Important medical events that may not result in death, be life-threatening, or require hospitalization may be considered an SAE when, based upon appropriate medical judgment, they may jeopardize the subject and may require medical or surgical intervention to prevent 1 of the outcomes listed above. Examples of such medical events include allergic bronchospasm requiring intensive treatment in an emergency room or at home, blood dyscrasias or convulsions that do not result in inpatient hospitalizations, or the development of drug dependency.

9.3 Serious Adverse Event Reporting – Procedures for Investigators

Initial Reports

All SAEs occurring from the time of informed consent (see Section 9.1) until 30 days following the last administration of study drug must be reported to Medpace Clinical Safety within 24 hours of the knowledge of the occurrence (this refers to any adverse event that meets any of the aforementioned serious criteria). All SAEs that the Investigator considers related to study drug occurring after the 30-day follow-up period must be reported to the Sponsor.

To report the SAE, complete the SAE form electronically in the electronic data capture (EDC) system for the study. When the form is completed, Medpace Safety personnel will be notified electronically and will retrieve the form. If the event meets serious criteria and it is not possible to access the EDC system, send an email to Medpace Safety at [contact] or call the Medpace SAE hotline (phone number listed below), and fax the completed paper SAE form to Medpace (fax number listed below) within 24 hours of awareness. When the EDC system becomes available, the SAE information must be entered within 24 hours of the system becoming available.

Safety Contact Information: Medpace Clinical Safety

Medpace SAE hotline – USA:

[contact], dial 3 or [contact], dial 3

[contact] or [contact]

E-mail: [contact]

Follow-Up Reports

The Investigator must continue to follow the subject until the SAE has subsided or until the condition becomes chronic in nature, stabilizes (in the case of persistent impairment), or the subject dies.

Within 24 hours of receipt of follow-up information, the Investigator must update the SAE form electronically in the EDC system for the study and submit any supporting documentation (eg, redacted subject discharge summary or autopsy reports) to Medpace Clinical Safety via fax or e-mail. If it is not possible to access the EDC system, refer to the procedures outlined above for initial reporting of SAEs.

